6.4.2.2 Additional Secondary Endpoints

6. The proportion of responders among BoNT/A-DP and placebo groups with a FWS score of 0 or 1 and an improvement ≥ 2 points in FWS score (at maximum frown) during the first treatment cycle visit relative to baseline, based on both the investigator's and the subject's in-clinic assessments (composite endpoint, at weeks 1, 2 and 8).
7. The proportion of subjects with ≥ 2 point reduction in FWS score (at maximum frown) in the BoNT/A-DP and placebo groups during the first treatment cycle visit relative to baseline, based on the independent rater's assessment of

- photographs (at baseline and visits 2, 4, 12, 16 and 20 weeks after treatment, within the first treatment cycle).
8. Time to onset of effect in the BoNT/A-DP and placebo groups in the first treatment cycle, as measured at weeks 1, 2 and 4 based separately on subject and investigator assessments. Onset of effect defined as at least a 1 point improvement in FWS score from baseline (at maximum frown). In addition, onset of effect will be assessed by subjects daily in the first 2 weeks after treatment, by recordings in the subject diary.
 9. The extent of subject perceptions of effect of, and satisfaction with, treatment, in the BoNT/A-DP and placebo groups, during each treatment cycle, as assessed by the FACE-Q Satisfaction with Outcome Scale.
 10. The proportion of subjects with a ≥ 1 point reduction in FWS score at rest in the BoNT/A-DP and placebo groups, relative to baseline, during the first treatment cycle, based on the independent rater's assessment of photos.
 11. The percentage of subjects with a FWS score of 0 or 1 and an improvement of ≥ 2 points in FWS score at maximum frown (investigator and subject assessment) at 4 weeks after re-treatment relative to the rating at the preceding end of cycle visit.

6.4.2.3 Safety

The secondary safety endpoints include:

1. Frequency, severity and causal relationship of AEs, SAEs and AESIs during the entire study period.
2. Antibody formation, evaluation pre-dose before each treatment, at 4 weeks after each treatment and at the final study visit.
3. Safety assessments by evaluating hematology, clinical chemistry, vital signs and ECGs as per study schedule (Section 2.1).

6.5 Randomization and Blinding

6.5.1 Randomization

This is a randomized, double blind, placebo-controlled efficacy and safety clinical study followed by an open label extension. Subjects will be randomly assigned to receive either BoNT/A-DP or placebo at a ratio of 3:1 respectively in the first treatment cycle. The 3:1 ratio in favor of active treatment versus placebo has been selected to increase the safety data base.

Randomization will be performed per study site via interactive web response system (IWRS). One unique randomization code will be assigned to each subject.

6.5.2 Blinding

For the first placebo controlled treatment cycle (the double-blind cycle of this trial), BoNT/A-DP and placebo will be provided to the sites in glass vials. Since BoNT/A-DP-vials contain a pellet of lyophilized BoNT/A-DP, they can be discerned from placebo-vials (empty vials). However, after reconstitution by an unblinded study team member at the site, both will look identical (clear solution, comparable volume), thus maintaining the blind. The unblinded study team member preparing the IMP at the study site must not, by any means, be involved in any other study data collection activities including AE assessment, case report form (CRF) completion, diary collection etc. IMP will be assigned to the subjects by IWRS with the lot number and kit number assigned corresponding to the group to which the subjects are assigned (blinded medication number and batch/lot number during the double-blind phase of the study at the given site). Once a subject has entered the open label extension, this unblinded study team member can then be involved in data collection activities with regard to that particular subject. The assigned vial will be reconstituted and will be forwarded to the investigator for injection. Specific Blinding Plans will be created at each study site during the Study Initiation visits, defining the Unblinded Study Team and the process of maintaining the blind by this Unblinded Study Team towards the blinded rest of the team.

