- 2 Evaluation for re-treatment takes place at the earliest at 12 weeks after the first/previous treatment. Subjects who do not qualify for re-treatment at week 12 will have the option (pending eligibility) for re-treatment at 4-weekly intervals thereafter, until they are eligible for re-treatment. Once the subject is eligible for re-treatment, the end of cycle procedures will take place and the subject can receive re-treatment (i.e. the end of cycle visit and the re-treatment visit will be conducted on the same day as the Evaluation for Re-treatment visit).
- 3 The latest time for re-treatment is study week 48; if a subject is not eligible for re-treatment at study week 48, the End of Study visit will be completed.
- 4 The End of Study visit can take place in four-weekly intervals from study-week 48 until study-week 60. For subjects receiving re-treatment at week 48, the last cycle will end 12 weeks later at week 60 (=End of Study visit). End of Study visit will take place at week 48 if week 48 visit is an Evaluation for Re-treatment visit and the subject is not meeting the criteria for re-treatment. For subjects having received their last injection 8 weeks or less prior to week 48, the End of Study visit will take place 12 weeks after the last study drug treatment was given, e.g. week 52 if subject was retreated at week 40. For subjects that get prematurely discontinued from the study (at any time) the End of Study visit will take place within 1 week of discontinuation.
- 5 Only in women of child-bearing potential; blood serum test at screening and End of Study visit; otherwise urine dip stick.
- 6 Vital signs include blood pressure (diastolic /systolic) and pulse.
- 7 Laboratory Assessments: Hematology and Serum Chemistry, details in Section 11.15.
- 8 Investigator's assessment of glabellar line severity at maximum frown and at rest. Assessment will be made using the 4-point FWS [GLS-I] (0 =none, 1=mild, 2=moderate, 3=severe) and will be recorded in the CRF.
- 9 Subject's assessment of glabellar line severity at maximum frown and at rest. Assessment will be made using the 4-point FWS [GLS-S] (0 =none, 1=mild, 2=moderate, 3=severe). Subject Assessment will be performed before (ideally) and always independently of investigator assessment and will be recorded in the CRF)
- 10 Photographs of subject's glabellar lines (at maximum frown and at rest) will be taken at C1 Randomization, C1 week 2, C1 week 4 and each C1 Evaluation for Re-Treatment visit

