7.3 Eligibility Criteria for Re-treatment

The following criteria **MUST** be met for re-treatment:

- At time of re-treatment subject does not have relevant changes to their health status from enrollment, which would have prevented subject's entry into the study according to the inclusion and exclusion criteria.
- The subject must have been randomized to receive treatment and must have received at least one treatment (BoNT/A-DP or placebo).
- A minimum of 12 weeks must have elapsed since the previous study treatment.
- The subject's glabellar lines at maximum frown must have relapsed to a FWS score of 2 or 3 as determined by both the investigator and the subject.
- No relevant infection or inflammation in the planned injection area.
- Negative urine pregnancy test, in women of child-bearing potential.
- The subject must have received fewer than four study treatments.
- The subject must agree and consent to re-treatment.
- Re-treatment will be performed at the latest by week 48.

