
Visit 4 C1 Week 2
	
14 days ± 2 days after Baseline (Day 0)
	
Collect Subject Diary (Section 9.4) FWS Subject self-assessment (GLS-S, Section 10.1.1) FWS Investigator (GLS-I, Section 10.1.1) Full physical examination (Section 11.11) AE and AESI assessment (Section 11)¹³ Concomitant medication (Section 11.10.1) Photography (Section 10.1.2)¹²
	

Visit 5 C1
	
4 weeks ± 2 days after Baseline
	
FWS Subject self-assessment (GLS-S, Section 10.1.1) Modified Skindex-16 (GL-QoL) and FACE-Q
	

Week 4	(Day 0)	Appraisal of Lines Between Eyebrows and Age Appraisal VAS scales (Section 20) FACE-Q Satisfaction with Outcome Scale (Section 20.6) FWS Investigator (GLS-I, Section 10.1.1) Full physical examination (Section 11.11) AE and AESI assessment (Section 11) ¹³ Concomitant medication (Section 11.10.1) Photography (Section 10.1.2) Vital signs (Section 11.13) ECG (Section 11.16) Antibody test (Section 11.15.2) Clinical laboratory assessments (Section 11.15)	
Visit 6 C1 Week 8	8 weeks ± 2 days after Baseline (Day 0)	FWS Subject Self assessment (GLS-S, Section 10.1.1) FWS Investigator (GLS-I, Section 10.1.1) AE and AESI assessment (Section 11) ¹³ Concomitant medication (Section 11.10.1)	
Visit 7 (or 7a, 7b, 7c) Evaluation for re-treatment Visit ⁴ End Of Cycle ⁵ Second treatment - entry to open label extension	12 weeks ± 2 days after Baseline (Day 0), with possible extension at 4-weekly (± 2 days) intervals until subject is eligible for re-treatment	FWS Subject self-assessment (GLS-S, Section 10.1.1) FWS Investigator (GLS-I, Section 10.1.1) AE and AESI assessment (Section 11) ¹³ Concomitant medication (Section 11.10.1) Confirmation of eligibility for re-treatment (Section 7.3) Photography (Section 10.1.2) Urine pregnancy test (if applicable, Section 11.12) Vital signs (Section 11.13) ECG (Section 11.16) Clinical laboratory assessments (Section 11.15) Antibody test (Section 11.15.2) Modified Skindex-16 (GL-QoL) and FACE-Q Appraisal of Lines Between Eyebrows and Age Appraisal VAS scales (Section 20) FACE-Q Satisfaction with Outcome Scale (Section 20.6) Eligibility for re-treatment (Section 7.3) ⁶ <hr/> Consent for re-treatment SECOND TREATMENT - OPEN LABEL (Section 8.3) Post-treatment observation and AE assessment over 30 minutes	
Visit 8	1 week ± 2 days after	AE and AESI assessment (Section 11) ¹³ Concomitant medication (Section 11.10.1)	

C2 Week 1	second treatment	Full physical examination (Section 11.11)	

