16.2.1 Case Report Forms

The investigator is responsible for the procurement and the quality of source data.

Authorized study site personnel will transcribe source data and source data changes to the CRF. All data should preferably be entered into the CRF on the day of the study visit, but no later than 2 working days thereafter. Changes to a CRF, if not self-evident, will require documentation of the reason for each change. After completion of the study, an electronic (or if necessary paper) version of the complete

set of CRFs for each subject will remain in the investigator file at the study site in accordance with the data retention policy (see Section 16.3).

The handling of data by the Sponsor, including data quality assurance, will comply with regulatory guidelines (e.g. ICH GCP). All data management activities will be conducted by the Sponsor's representative who will follow their SOPs. Data management and control processes specific to the study will be described in the Data Management Plan.

Once all the Data Quality Control steps have been performed, the database will be locked and the records will be released for reporting and statistical analysis. Data will be transferred to the study sites via CDs and transferred to the study Sponsor via an external hard drive. The media will contain subject PDF files of the electronic CRFs.

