16.3.1 Data Base Lock

The data base will be locked after all data of the first treatment cycle and of the open label extension phase are entered into the CRF, the data base is confirmed as ‘clean’, and the data review meeting has taken place. Further details will be described in the Data Management Plan.

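### The unblinded preparer's release at open-label entry is not limited to open-label data, leaving cycle 1 adverse event records within reach until the single study-end lock

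*Protocol*

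**What the plan says.** Active and placebo vials can be told apart before reconstitution, so the person who prepares them knows the allocation. During the double-blind cycle, Protocol 6.5.2 says that this person "must not, by any means, be involved in any other study data collection activities including AE assessment", and it names CRF completion and diary collection as well. The bar is then lifted subject by subject: after entry to the extension, "this unblinded study team member can then be involved in data collection activities with regard to that particular subject". SAP 3.2.2 repeats the text. Neither document confines the release to records from cycles 2 to 4.

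Three other provisions bear on this:

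- **Timing of entry.** Under the footnotes to Protocol 2.1, "the end of cycle visit and the re-treatment visit will be conducted on the same day as the Evaluation for Re-treatment visit". The visit 7 entry in Table 9-1 also lists AE and AESI assessment.
- **CRF entry (Protocol 16.2.1).** "All data should preferably be entered into the CRF on the day of the study visit, but no later than 2 working days thereafter".
- **Lock (Protocol 16.3.1).** "The data base will be locked after all data of the first treatment cycle and of the open label extension phase are entered". Protocol 12.5 likewise places the analysis of both phases after one lock at the end of the study. No earlier freeze of cycle 1 is described.

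**The concern.** Cycle 1 is the only period with a concurrent placebo group. Secondary safety endpoint 1 (Protocol 6.4.2.3) covers how often adverse events occur, how severe they are and whether they are causally related. Severity and causality are judgments, and onset dating can be one too, so blinding of the people who make and handle these records matters.

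The blinding rule is strict up to the switch and then stops altogether for that subject, although the subject's cycle 1 records are still open. The person released is the one person at the site who knows by design what the subject received in cycle 1. At stake is the credibility of the placebo comparison of adverse events and, to a lesser degree, of any cycle 1 record amended after the switch.

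**Working it through.** The plan gives no figure to reproduce for this point. The check sets the provisions side by side.

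**1. Scope of the release.** The trigger is the subject's entry to open label, and the permission covers data collection for that subject. No data period is mentioned in Protocol 6.5.2 or SAP 3.2.2.

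**2. Cycle 1 adverse event data that can still change after the trigger.**

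- Events assessed at the entry visit can reach the CRF up to 2 working days later (Protocol 16.2.1), when the bar has already lapsed.
- A change in severity of an ongoing event is written as a new row with its own dates and relationship (Protocol 11.6). Events are allotted to cycles by start date, so the date given to the change decides on which side of the injection the row falls.
- Causality of an SAE or AESI may be revised on follow-up (Protocol 11.6.1).
- An event whose incomplete onset date cannot be placed is counted in cycle 1 (Protocol 12.4.2, SAP 8.7.2), even if first recorded after the switch.
- The term investigator includes study personnel designated for a duty (Protocol 14.1), so these tasks can be delegated.

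**3. How long the records stay open.** For one subject switching at week 12 and ending at week 60: 60 − 12 = 48 weeks. The lock is study-wide, so this understates the period for early enrollees. The Synopsis plans up to 23 months from first to last visit, or 23 × 52/12 ≈ 99.7 weeks. For a first subject with 2 weeks of screening who switches at week 12, that leaves 99.7 − 2 − 12 ≈ 86 weeks to the last visit, with lock later still. This illustrates the planned timelines; it does not measure how much editing would occur.

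**4. Existing safeguards.**

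| Safeguard | Covers | Leaves open |
|---|---|---|
| Blinded transcription (Protocol 9.4.1, 9.4.2) | Diary and questionnaires | AE forms; later queries and amendments |
| Audit trail (Protocol 16.2) | All changes | Records a change but does not prevent it |
| Site blinding plans (Protocol 6.5.2) | Conduct at each site | Not among the documents; written under the same permissive rule |

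**5. Does the same-day switch reach key secondary endpoints 1, 2 or 4?** To be re-treated, the subject's lines at maximum frown "must have relapsed to a FWS score of 2 or 3 as determined by both the investigator and the subject" (Protocol 7.3). A responder needs a score of 0 or 1, with at least 2 points of improvement, from both raters (Protocol 6.4.1.1). Taking baseline 2 or 3 and entry-day 2 or 3 for each of the two raters gives 2 × 2 × 2 × 2 = 16 combinations, of which 0 are responders. Re-treatment before week 16 or week 20 makes the subject a non-responder at that visit by rule (Protocol 12.4.2). Any rating that counts as a response was made at an earlier visit, at least 4 weeks before entry, while the bar applied. The same-day route is therefore closed for these endpoints.

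**The case against.** The strongest reply is that the sentence plainly means the preparer may help with data from open-label entry onward. The entry-day assessments come before the injection, and the severity ratings are made by the blinded investigator and the subject. Questionnaire entries must be transcribed by blinded staff; Protocol 9.4.2 lists the FWS among these instruments, and sections 20.1 and 20.2 call both rating forms questionnaires. Causality is the investigator's task (Protocol 11.5.1), changes are tracked, and safety is analyzed descriptively without tests. The site blinding plans, which are not available here, may already deal with this.

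Most of this stands as mitigation. It does not remove the gap: the text does not state the restriction, AE forms and queries have no blinded-entry rule, and investigator duties can be delegated. A descriptive comparison can also be biased.

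A reader might infer more than the documents support:

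- **That the confirmatory responder endpoints are compromised because rating and release share a day.** Step 5 of the working shows they are not. What remains for efficacy is later amendment of an earlier cycle 1 record, which the audit trail would show.
- **That end-of-cycle questionnaires are exposed.** Their initial entry is reserved for blinded staff, and key secondary endpoint 5 is measured at week 4.
- **That Protocol 6.5.3 is contradicted.** That section concerns revealing the assignment. The preparer already knows it, and the release discloses it to nobody else.
- **That nearly all 175 placebo subjects switch at week 12 and the lapse therefore differs by arm.** The documents give no switching rate. The release also never applies to subjects who do not enter open label.

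**Conclusion.** The point holds as a minor weakness in the blinding rule. After a subject's switch, a person who knows the cycle 1 assignment is permitted to assess, query or amend that subject's cycle 1 adverse event records, and to amend other cycle 1 records, until the study-end lock.

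No bias size can be derived: the documents do not say how many cycle 1 events would be open at the switch, how often records would be amended, or how sites would use the permission. The conclusion rests on reading the release as written, without an implied limit to open-label data, and on the absence of a stated cycle 1 freeze or AE entry restriction. If the site blinding plans already impose that limit, only the wording of the protocol and SAP needs aligning. No sample size, endpoint or analysis is affected.

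**What to change.** In Protocol 6.5.2 and SAP 3.2.2, replace the subject-level release with a data-level one:

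- After a subject's open-label injection, the unblinded member may handle only data generated from that injection onward.
- Entry, queries and amendments of cycle 1 forms, and of adverse events with onset in cycle 1, stay with blinded staff until database lock. This should include events that the incomplete-date rule would place in cycle 1.
- Enforce this through EDC role permissions, and carry the same wording into the site blinding plans.

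The cost is a wording change in the documents and blinding plans, an EDC permission setting, and slightly less staffing flexibility at small sites. Visits and assessments are unchanged.

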6.5.3 Unblinding

The decision to unblind lies fully with the investigator. The randomization assignment should not be revealed before the study has been completed and the database has been cleaned and closed. The study will be unblinded using the Study Specific Unblinding Procedure (an unblinding module is standard on all blinded studies; also it is possible to grant access to regulatory unblinding users so that they can monitor the safety of the study, if required).

In case of emergency, the IMP administered to the subjects can be revealed using the unblinding function of the IWRS.

In rare emergencies, unblinding may be necessary for the clinical management of an AE. Investigators should consider unblinding only if knowledge of the administered product will have an influence on the further treatment of the AE. In such events, the investigator should make every attempt to inform the Sponsor before breaking the blind or as soon as possible after unblinding has been performed. The [REDACTED] or CROMA medical team is available to discuss any unblinding need. However, such discussion is not mandatory. The investigator can always unblind as per his/her discretion if the actual treatment information is considered relevant for subsequent

event treatment. Once unblinding has occurred, the site should immediately contact the [REDACTED] or CROMA medical team. Communication of the unblinding result is considered acceptable. It is at the discretion of the investigator to continue an unblinded subject in the study. The date and time of breaking the code, the reason for breaking the code, study product administered, subject identification number and randomization code will be documented within the IWRS.

6.6 Study Stopping Rules

In a case of critical non-compliance of site to ICH Good Clinical Practice (GCP), the study protocol, the Declaration of Helsinki, or any applicable regulation, the Sponsor may stop the entire study or participation of a study site at any time. In addition, the Sponsor may stop the entire study, or terminate participation of a study site for any medical reason at any time.

In the event of individual subject's premature study termination resulting from an AE, refer to Section 9.5.

Premature termination of a subject

A subject must be terminated from the study if any of the following occur:

- Withdrawal of informed consent.
- Treatment with any other investigational product in another clinical study.
- Treatment with any BoNT other than study medication.
- Pregnancy (with follow-up until the end of the current treatment cycle).
- Any significant treatment-related side effects where treatment continuation would constitute an unacceptably high risk for the subject.

Premature termination of a site or of the entire study

A site or the entire study may be terminated if any of the following occur:

- Critical non-compliance to ICH GCP, the study protocol, the Declaration of Helsinki, or any applicable regulation.
- The positive benefit/risk ratio is no longer maintained.
- The Sponsor may stop the entire study for any medical reason at any time.
- The Sponsor can terminate the study or a study site at any time for any other reason.

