If at an Evaluation for Re-treatment visit the subject wants to get re-treated, but the investigator does not agree or vice versa (i.e. the FWS score is not \geq at least 2 by both assessments), the subject will return to the site 4 weeks thereafter for another Evaluation for Re-treatment visit. There is no limit to the number of Evaluation for Re-treatment visits. In order to consider a visit as the End of Cycle visit, there must always be agreement between investigator and subject on a FWS score (at maximum frown) of ≥ 2 .

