6.3.3 End of Study Visit

The End of Study visit can take place in four-weekly intervals from study-week 48 until study-week 60. The last study drug re-treatment will be administered no later than week 48. For subjects receiving a re-treatment at week 48, the last cycle will end 12 weeks later at week 60 (i.e. End of Study visit).

The End of Study visit will take place at week 48, if the week 48 visit is an Evaluation for Re-treatment visit and the subject does not meet the criteria for re-treatment i.e. this visit is 12 or more weeks after the last treatment. As week 48 is the last possible time point for re-treatment, such subjects will continue with all additional assessments of the End of Study visit on the same day. For subjects having received their last injection 8 weeks or less prior to week 48, the End of Study visit will take place 12 weeks after the last study drug treatment was given, e.g. week 52 if the subject was re-treated at week 40.

For subjects who are prematurely discontinued from the study (at any time), the End of Study visit will take place within 1 week of discontinuation.

The number of treatments administered per subject will depend on the subject's qualification for re-treatment. A maximum of four study treatments may be administered per subject, with the last opportunity for re-treatment being week 48. A

subject will be followed-up until he/she would qualify for re-treatment (if below 48 weeks), since there is no maximum time frame for re-treatment.

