7.4 Withdrawal and Discontinuation

A subject may voluntarily withdraw from study participation and data collection for any reason at any time (withdraw consent). A subject will be considered lost to follow-up when at least three unsuccessful attempts to contact the subject have been documented.

Every effort will be made to have the withdrawn/discontinued subject complete the End of Study visit (see Section 6.3.3). The reason for withdrawal/discontinuation will be recorded on the CRF (see Section 9.5).

In the event of discontinuation due to an AE/SAE, clinical and/or laboratory investigations that are beyond the scope of the required study procedures may be performed as part of the evaluation of the event. Any subject withdrawn due to an AE, SAE or clinically significant abnormal laboratory test value will be evaluated by the investigator and will be treated and/or followed up until the symptoms or values return to normal or acceptable levels, as judged by the investigator, or until values are stable, a plausible explanation has been provided, or the subject has received another injection with botulinum toxin outside the study.

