⁸ A maximum of four treatments per subject (four treatment cycles) is permitted during the study time frame, with treatments separated by a minimum of 12 weeks. There is no limit to the number of Evaluation for Re-treatment visits.

⁹ The End of Study visit can take place in four-weekly intervals from study-week 48 until study-week 60. For subjects receiving re-treatment at week 48, the last cycle will end 12 weeks later at week 60 (=End of Study visit). End of Study visit will take place at week 48 if week 48 visit is an Evaluation for Re-treatment visit and the subject is not meeting criteria for re-injection. For subjects having received their last injection 8 weeks or less prior to week 48, the End of Study visit will take place 12 weeks after the last study drug treatment was given, e.g. week 52 if the subject was retreated at week 40. A \pm 2 day time window is always applied for conducting the End of Study visit.

¹⁰ For subjects that are prematurely discontinued from the study (at any time), the End of Study visit will take place within one week of discontinuation. For subjects terminating the study early as per decision made at a site visit, the study procedures required at the End of Study visit should be performed at the visit during which the subject was terminated from the study.

¹¹ In subjects who do not receive any additional treatments, assessments already performed that day do not need to be repeated if both visits take place on the same day.

¹² Photographs of subject's glabellar lines will be taken at C1 Randomization, C1 Week 2, C1 Week 4 and each C1 Evaluation for Re-Treatment visit in Cycle 1 until the subject qualifies for re-treatment in order to provide evidence of effect and confirm that the subject did not qualify for re-treatment on the preceding Evaluation for Re-treatment visit. Although a photograph will be taken at each Evaluation for Re-treatment visit, only the photo of the visit preceding the re-treatment visit will be reviewed by the independent reviewers

¹³ AESI Questioning: active questioning by guided review of systems (ROS) as per AESI manual. If an AESI is reported, a targeted physical examination around the area of the reported AESI must follow.

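### Protocol 6.6 can be read to end study participation mid-cycle for significant treatment-related side effects, so new non-serious AEs and AESIs go uncollected for the rest of the 12-week schedule

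*Protocol*

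**What the plan says.** Protocol Section 6.6 (Study Stopping Rules) lists the events for which a subject has to leave the study. One is "Any significant treatment-related side effects where treatment continuation would constitute an unacceptably high risk for the subject". No follow-up period is attached. The pregnancy bullet in the same list does keep follow-up to the end of the current cycle.

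Three places set what happens next:

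- Section 6.3.3: for premature discontinuation, the End of "Study visit will take place within 1 week of discontinuation".
- Section 2.1, footnote 4 (repeated in SAP Table 1, footnote 4): for subjects "prematurely discontinued from the study (at any time) the End of Study visit will take place within 1 week of discontinuation".
- Table 9-1, footnote 10: if the decision is made at a site visit, the End of Study procedures "should be performed at the visit during which the subject was terminated from the study".

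Section 9.5, to which 6.6 refers for AE terminations, asks for the End of Study visit and the reason for stopping. Under Sections 11.1 and 11.6.1, AE recording and AESI reporting run from consent to the End of Study visit.

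Some follow-up continues after that visit. Under Section 7.4, a subject withdrawn because of an AE "will be treated and/or followed up until the symptoms or values return to normal or acceptable levels", with stability or a plausible explanation among the other end points. Section 11.6 follows every event ongoing at End of Study until it resolves or stabilises. Section 11.6.1 requires later SAEs to be reported if they are at least possibly related.

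**The concern.** Each cycle consists of one injection session. A subject terminated at week 1, 2, 4 or 8 has already had the full exposure of that cycle, so leaving the study removes no risk in that cycle. It does remove the remaining directed AESI questioning while the toxin may still be acting.

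Toxin spread is the safety issue singled out in Sections 4.6.2 and 11.2, and these subjects have already shown a significant treatment-related effect. A new, separate, non-serious event starting after the End of Study visit (mild diplopia, for example) would not be collected.

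The possible consequence is some understatement of TEAE and AESI event counts and preferred-term rates in the tables of SAP 8.7.2. The proportion with any TEAE is unaffected, because the trigger already counts. The proportion with any AESI changes only if the trigger was not itself an AESI.

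**Working it through.** **The plan's own follow-up arithmetic.** Section 6.3.3 states that for late re-treatments "the End of Study visit will take place 12 weeks after the last study drug treatment was given". Last treatment at week 48: 48 + 12 = 60. At week 40: 40 + 12 = 52. Both match the text.

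**Gap after mid-cycle termination.** Inputs are the minimum cycle of 12 weeks (Section 2.2), safety contacts at weeks 1, 2, 4, 8 and 12 (Section 2.1), and a lag L from termination to End of Study of 0 weeks (Table 9-1, footnote 10) to 1 week (Section 6.3.3). For termination at week t, the gap is 12 − (t + L), not below 0.

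| Termination week t | End of Study week | Gap in weeks (L = 1 to L = 0) | Scheduled contacts after t |
|---|---|---|---|
| 1 | 1–2 | 10–11 | 2, 4, 8, 12 (four) |
| 2 | 2–3 | 9–10 | 4, 8, 12 (three) |
| 4 | 4–5 | 7–8 | 8, 12 (two) |
| 8 | 8–9 | 3–4 | 12 (one) |
| 12 (re-treatment visit) | 12–13 | 0 | none |

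The lost contacts are replaced by at most one End of Study visit.

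**Sensitivity to the window.** The documents give no onset window for adverse events. Section 4.4.1 puts nerve recovery at two to three months: 60.9/7 = 8.7 weeks to 91.3/7 = 13.0 weeks. Taking the shorter window with L = 1 and the longer with L = 0:

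- Week 1: 8.7 − 2 = 6.7 to 13.0 − 1 = 12.0 weeks
- Week 4: 8.7 − 5 = 3.7 to 13.0 − 4 = 9.0 weeks
- Week 8: 0 (8.7 − 9 is negative) to 13.0 − 8 = 5.0 weeks
- Week 12: 0 to 13.0 − 12 = 1.0 week

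**How many subjects.** The documents give no rate for this trigger. Assume that severe treatment-related events stand in for it. Section 4.4.2.1 reports none among 134 subjects on BoNT/A-DP. The one-sided 95% upper limit is 1 − 0.05^(1/134) = 0.0221, and 0.0221 × 525 = 11.6. That is 0 to about 12 subjects in cycle 1, counting terminations and not missed events. If every moderate event there (six) were also a trigger, the rate would be at most 6/134 = 4.5%, and 0.0448 × 525 = 23.5, about 24. The unacceptable-risk wording makes that unlikely.

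**How many events.** The same study had 33 treatment-related events in 134 + 137 = 271 subjects over 16 weeks. Assume 12 subjects, all terminated at week 1 with a same-day End of Study visit, and even onset: 12 × (33/271) × (11/16) = 1.0 event. At three times that rate, because these subjects have already reacted, it is about 3.

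**The case against.** The strongest reply is that the trigger speaks of continuing treatment. With one injection per cycle, the next treatment decision comes at week 12 or later, when Section 7.3 re-checks health status. On that reading nothing is lost. This stands as a possible reading, and it is why the point is conditional. However, Section 6.6 requires termination when the event occurs, and footnote 4 of Section 2.1 allows discontinuation at any time, so mid-cycle use is also permitted.

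A reader might infer that subjects harmed by the product are left without safety follow-up, or that serious toxin spread would be missed. The documents do not support that. Sections 7.4 and 11.6 follow the trigger and all other ongoing events. Related SAEs stay reportable, and Section 11.3 counts important medical events as SAEs.

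A reader might also take 10–11 weeks as time at risk. It is not: it is the worst row of a schedule. The 12 weeks matches the efficacy duration anticipated in Section 6.1, and the recovery range comes from the non-clinical summary. Neither is an AE onset window.

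The subject count is also weakly anchored. Severe is a grade and the trigger is not, and the count of 12 covers cycle 1 only although up to four treatments are possible. This objection stands: the count indicates scale and does not bound the whole study.

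**Conclusion.** The gap is real if Section 6.6 is applied mid-cycle: 10–11 weeks of the 12-week schedule at week 1, falling to 3–4 at week 8 and 0 at a week-12 re-treatment visit. It covers only new, distinct, non-serious AEs and AESIs that start after the End of Study visit. On the stated assumptions, this means roughly a dozen subjects at most in cycle 1 and one to three missed related events.

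Safety variables are summarised descriptively (Protocol 12.4.2). A subject terminated before week 4 with no week-4 score counts as a non-responder, but with so few subjects the effect on the primary comparison is negligible. The documents do not support reading this as a threat to any trial conclusion. It is a low-severity improvement, worth making because it is cheap and concerns the hazard that the protocol itself singles out.

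**What to change.** Keep the clinical criterion. For this bullet, unless consent is withdrawn, replace termination with:

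*No further study injections; continue the scheduled visits and calls, with all scheduled assessments including AE/AESI and FWS, until 12 weeks after the last injection, then the End of Study visit (same day if 12 weeks have already passed).*

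Do not borrow the pregnancy wording. Before week 48 a cycle has no fixed end: Section 6.3.2 says "There is no limit to the number of Evaluation for Re-treatment visits", and Section 6.3.3 follows subjects until they would qualify, "since there is no maximum time frame for re-treatment". The 12-week rule already exists in 6.3.3.

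Align the following:

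- Protocol 6.3.3, 7.4 and 9.5; Section 2.1 footnote 4; Table 9-1 footnote 10.
- The timing cell for Visit 22 in Table 9-1. It puts End of Study on the same day once no further treatment is possible, so left unchanged it would undo the fix.
- SAP 3.3 and SAP Table 1 footnote 4.
- SAP 8.2 and 8.7.2: state that these subjects count as discontinued from treatment because of the AE, so that the disposition and leading-to-discontinuation tables stay clear.

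With 6.6 itself, that is 7 places in the protocol and 4 in the SAP. No new visit type is needed, and Section 11.5.4 already lets the site record that study drug was discontinued. The burden is at most four more already scheduled contacts for a few subjects, the last being the End of Study visit.
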